# 1.3. Limitations of the study design

Potential limitations of the study are related to the use of claims data, especially the completeness of prospectively accrued data and the paucity of clinical or biological data.

The SNDS provides clinical information about a specific disease only through coded discharge diagnoses and recorded Long Term Illnesses (ICD-10 codes), and the drug and medical devices used. The identification of patients with a certain disease or comorbidity often depends on the development of algorithms taking into account different combinations of hospital diagnoses or types of delivered drugs.

The SNDS does not provide paraclinical information and other risk factors such as smoking, weight, or body mass index (except when coded within hospitalization data). For the present study, no subgroup can be defined to assess mepolizumab exposure according to weight/bmi. However, age and sex subgroups can be defined. Drug related adverse events are not reported in the SNDS, so traditional safety analyses are not possible.

Mepolizumab exposure is based solely on its delivery; the actual exposure of the patient to the delivered drug is not measurable in this secondary database study, and this limitation should be mentioned in subsequent publications.

The overwhelming strength of the SNDS database is that it is one of the largest continuous countrywide claims databases. It covers just about the whole population (99%) essentially from birth to death, irrespective of the health care provider, age or socioeconomic status, and retirement status (Bezin et al. 2017). Patients keep the same identifier throughout their lifetime, and there are no restrictions in coverage related to income or social situation. At this point about 600 million patient years of data are stored, though not all are immediately accessible.

There are no risks to patients associated with study execution or study findings.

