### Describing the population

The index date "T0" is defined as the day upon which the beneficiary received a first dose of mepolizumab. Population characteristics will be tabulated at this time point and will include age, gender, area and region of residency, universal medical coverage status, and complementary health insurance status.

The population will be further described by providing the duration of treatment with mepolizumab (ie medication persistence (Cramer et al. 2008), defined as date of last administration – T0 in days) as well as the proportion of days of follow-up covered (PDC) by mepolizumab. The current authorized dosage for mepolizumab is a single 100 mg subcutaneous injection every 4 weeks (with an authorized leeway of +- 7 days), and the PDC will be determined accordingly.

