#### **Consultations**

The cumulative numbers of consultations will be compared between the baseline and exposure period and differentiated according to type (general and specialist medical consults, nursing and other paramedical consults etc). Special attention will be given to pulmonology/allergology and metabolic/endocrine specialist consults, as well as nursing consults for injections.

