### Assessments/procedures

Information concerning the laboratory and imaging assessments performed is available, but not their results. Special attention will be given to lung function, adrenal function, glycemia, and bone

density assessments. The cumulative numbers of different assessments will be described and contrasted between the baseline and exposure periods.

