# 3. Study Design

## 3.1. Overall Design

This retrospective, non-interventional (not involving human subjects) database study will compare real-life patient health resource consumption before versus after a first injection of mepolizumab. Data concerning patients receiving mepolizumab will be collated for a 12-month period (the "baseline period") preceding a first index treatment (at "T0") and compared to a 12-month period occurring after the index treatment (the "exposure period")(Figure 5-1).

[figure not shown]

Figure 3-1 Graphic presentation of the basic study design comparing health care resource use data between a one-year baseline period and a one-year exposure period after the first administration of mepolizumab (T0).

The expected correspondence to calendar time (Figure 5-2) is an inclusion period for T0 starting in February 2018 to December 2018, with 12 months of "follow-up" corresponding to the year 2019. It follows that baseline data will reach back to February 2017. If data for exposure periods longer than 12 months are available, these will also be collected to describe future trajectories of health resource use in as much as possible.

Figure 3-2 The expected correspondence with real time is an inclusion period covering patients who started mepolizumab in the year 2018, with 12 months of "follow-up" in the year 2019.

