# 4. Study Population

The study population will comport all beneficiaries in the national French SNDS database who were prescribed mepolizumab and for whom health resource use data is available for the 12 months preceding and following a first filled prescription for mepolizumab.

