### 4.2. Exclusion Criteria

- Health resource use data covering the 12 months preceding the first filled prescription for mepolizumab are not available
- Health resource use data covering the time period starting at the first filled prescription for mepolizumab and ending at subsequent death or at 12 months later are not available

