# 10. Appendices

# **Appendix 1: Abbreviations and Trademarks**

CEREES: Comité d'Expertise pour les Recherches, les Études et les Évaluations dans le domaine de la Santé; Evaluation committee for research, studies and evaluations in the field of health

CNAMTS: Caisse Nationale d'Assurance Maladie des Travailleurs Salariés; French National Health Insurance for Employees

CNIL: Commission Nationale de l'Informatique et des Libertés. The French data protection commission

COPD: chronic obstructive pulmonary disease

CS: corticosteroid

EnCEPP: European Network of Centers for Pharmacoepidemiology and Pharmacovigilance

ICS: inhaled corticosteroid

LABA: long acting beta antagonist

OCS: oral corticosteroid

PDC: proportion of days of follow-up covered by mepolizumab

PMSI: Programme de Médicalisation des Systèmes d'Information. A French national hospitalizations database.

SABA: short acting beta antagonist

SNDS: Système National des Données de Santé. National Health Data System in France.

SNIRRAM: Système National d'Information Inter Régimes de l'Assurance Maladie. The main national claims database in France.

T0: The time of the first mepolizumab administration.

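### The baseline year runs right up to T0, so care that leads to mepolizumab counts as untreated use and biases the specialist consultation and assessment contrasts towards a fall of unknown size

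*Protocol*

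**What the plan says.** Section 3.1 sets the baseline as the 12 months preceding the index treatment at T0 and the exposure period as 12 months after it. It states no gap between them.

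The index is described in two ways:

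- **First dose.** Section 2 (Describing the population) says that T0 "is defined as the day upon which the beneficiary received a first dose of mepolizumab". Appendix 1 gives "The time of the first mepolizumab administration", and sections 3.1 and 5.6 agree.
- **First filled prescription.** Section 4 requires patients "for whom health resource use data is available for the 12 months preceding and following a first filled prescription for mepolizumab". Section 4.2 excludes a patient if "Health resource use data covering the 12 months preceding the first filled prescription for mepolizumab are not available".

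Section 1.3 adds that "Mepolizumab exposure is based solely on its delivery".

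The outcomes at issue are in section 2. For consultations, "Special attention will be given to pulmonology/allergology and metabolic/endocrine specialist consults, as well as nursing consults for injections". For assessments, where lung function is among those singled out, "The cumulative numbers of different assessments will be described and contrasted between the baseline and exposure periods". Section 8.3.2 compares the two periods with paired t-tests or paired Wilcoxon tests. The objectives table makes health resource use secondary and total cost primary.

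**The concern.** A prescription is written on or before the day it is filled, and the drug is given on or after that day. Unless everything happens on one day, the prescribing contact lies before the index. So do any lung function tests, imaging or laboratory work done to reach the decision. With no gap, all of this enters the year that is meant to show use without mepolizumab. It can do so even in a patient whose disease is stable, so it is a separate matter from regression to the mean.

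Section 1.1 speaks of changes attributable to mepolizumab, and section 2 states the hypothesis that treatment lowers resource use. The bias runs in favour of that hypothesis, for outcomes the protocol singles out. All patients are treated (section 5.3), so no comparison group would reveal it. The false discovery rate correction in section 8.3.2 deals with multiplicity and not with bias. Section 1.3 does not list the problem as a limitation.

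**Working it through.** **1. Does the mechanism depend on the anchor?** No.

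- Indexed on the fill, the baseline ends at the fill, and a prescribing visit on any earlier day lies inside it.
- Indexed on the dose, the baseline ends on the same day or later, so any care between fill and dose is added to it.
- A visit on the index day itself is not assigned to either period.

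**2. The protocol's own precision (section 8.1).** Expected n = 29 × 97 = 2813, and √2813 = 53.04. For a paired t-test at two-sided α = 0.05 and effect size d = 0.063:

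- d × √n = 0.063 × 53.04 = 3.34.
- Power ≈ Φ(3.34 − 1.96) = Φ(1.38) = 91.6%.
- Effect detectable with 90% power: (1.960 + 1.282) / 53.04 = 0.0611. For the Wilcoxon test with relative efficiency 3/π it is 0.0625.

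The stated 90% or better at 0.063 is reproduced.

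**3. What net excess would be flagged?** The documents give no visit counts, no SDs and no interval from prescription to fill. The SD of the within-patient change is therefore assumed. The net excess is the pre-T0 initiation visits that are additional to usual care, less any extra visits after T0. The excess flagged with 90% power is 0.0611 × SD:

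| Assumed SD of paired change (visits) | Net excess flagged with 90% power |
|---|---|
| 2 | 0.12 |
| 4 | 0.24 |
| 6 | 0.37 |
| 8 | 0.49 |
| 10 | 0.61 |

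A net excess of one visit per patient reaches 90% power for any SD up to about 16 (1 / 0.0611 = 16.4).

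**4. When would it not be flagged?** A net excess of 0.1 visit with SD 4 gives d = 0.025 and d × √n = 1.33. Power is Φ(1.33 − 1.96), about 26%. With SD 8 it is about 10%.

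**5. Does the plan remove it?** Section 8.3.3 uses a 28-day sliding window, but for the cost-rate curve. Mean cumulative functions for events can be computed, for uses found to differ before and after T0. They might show a rise before T0, but they are optional and leave the paired contrast of section 8.3.2 unchanged.

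**The case against.** The strongest reply is that any before-after study indexed on treatment start has this feature, and that a sensitivity window is the kind of detail a statistical analysis plan would carry. The first part is true, but it does not remove the bias. On the second, the protocol itself fixes the windows, names the outcomes and sets the contrast.

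Three further objections stand, and they limit the point.

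- **A prescribing visit need not be an additional visit.** A patient under regular specialist follow-up may receive the prescription at an appointment that would have taken place anyway. The excess is then zero.
- **Follow-up after T0 acts the other way.** If the excess before T0 is one visit, one extra specialist review in the exposure year cancels it in the observed contrast, and two reverse its sign.
- **The primary endpoint is little affected.** Section 8.3.3 expects a marked rise in the cost slope at T0 from mepolizumab itself. The cost of a visit and some tests is probably small beside it.

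Two stronger readings are tempting. From section 4, a reader might infer that T0 is the first filled prescription. That section states a data-availability condition, and T0 is defined as the first dose. A reader might also infer that a fall is built in and almost certain to be significant. Assuming 0.5 to 1.0 extra visit and an SD of 2 to 5 gives d from 0.5/5 = 0.10 to 1.0/2 = 0.50, and z from 5.3 to 26.5. Those values follow only from the chosen inputs and from assuming no change after T0. The documents support neither.

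**Conclusion.** The concern holds as a bias of known direction and unknown size. Care that leads to mepolizumab is counted as untreated use, which pushes the consultation and assessment contrasts towards a fall, and nothing in the paired comparison removes or examines this. At the expected sample size, a net excess of a fraction of a visit per patient can be enough to give a significant result, but only under assumed SDs. With a smaller excess or a larger spread it would probably go unnoticed. The net result could also be zero or a rise. The point concerns secondary endpoints, and no material effect on primary total cost is shown. Separately, the dose anchor and the filled-prescription anchor need to be reconciled.

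**What to change.** 1. Use one index date throughout sections 2, 3.1, 4, 4.2, 5.6 and Appendix 1, and state which period the index day belongs to.
2. Add to section 8.3.2 a companion analysis for consultations and assessments that leaves out a window before T0, for example 28 and 91 days. These lengths are assumptions and should be labelled so. Compare rates per person-time, and give the full 12-month baseline as a rate too, so that only the window changes.
3. Show monthly counts of these contacts across T0.
4. If a fall does not remain, report that it cannot be separated from care around treatment initiation, and do not attribute it to mepolizumab. A fall that disappears does not prove that initiation contacts caused it.
5. Add the limitation to section 1.3.

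The cost is one set of tables and a figure. Section 2 lists dated visits, procedures and laboratory tests as available in the SNDS, so no new data are needed. The downside is small: the shortened baseline loses its calendar-month match with the exposure year and drops some genuine untreated use. The analysis should therefore supplement the main contrast and not replace it.

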#### 4.1. Inclusion Criteria

- Beneficiary in the anonymous French national SNDS database
- The beneficiary received mepolizumab

### 4.2. Exclusion Criteria

- Health resource use data covering the 12 months preceding the first filled prescription for mepolizumab are not available
- Health resource use data covering the time period starting at the first filled prescription for mepolizumab and ending at subsequent death or at 12 months later are not available

# 4.3. Lifestyle Restrictions

No restrictions are required.

## 4.4. Screen Failures

Not applicable.

### 5. Treatments

Study treatment is defined as any investigational treatment(s), marketed product(s), placebo, or medical device(s) intended to be administered to a study participant according to the study protocol.

### 5.1. Treatments Administered

Not applicable. This is an observational database study during which no drugs are administered. The data do however concern beneficiaries of the French medical system who received mepolizumab in the past.

### **5.2.** Dose Modification

Not applicable to the present database study.

## **5.3.** Method of Treatment Assignment

Only data for beneficiaries who received mepolizumab will be analyzed. Therefore, 100% of the statistical observations / beneficiaries in this study will have received mepolizumab in the past.

# 5.4. Blinding

Not applicable to the present database study.

# 5.5. Preparation/Handling/Storage/Accountability

Not applicable to the present database study.

# **5.6.** Treatment Compliance

Medication persistence is defined as the duration from T0 (first injection of mepolizumab) to the discontinuation of therapy (Cramer et al. 2008).

The proportion of days of follow-up covered (PDC) by mepolizumab will also be calculated as the best available proxy for adherence and an important covariate for analyses.

# **5.7.** Concomitant Therapy

All drug consumption available in the SNDS will be analyzed, with specific attention given to (i) mepolizumab, (ii) corticosteroids (oral/IV/systemic, inhaled, topical, etc), asthma-specific medications (selective beta-2-adrenoreceptor agonists, adrenergics in combination with corticosteroids or other drugs, anticholinergics, adrenergics for systemic use, xanthines, leukotriene receptor antagonists, other systemic drugs for obstructive airway diseases, etc), and diabetes-related medications (buiguanides, insulin, etc). Drugs demonstrating significant changes in cumulative dose between the baseline and exposure periods (if any in addition to mepolizumab) will be identified.

# **5.8.** Treatment after the End of the Study

Not applicable to the present database study, which is completely observational and will not affect past, current or future practice/treatment in any way.

#### 6. Discontinuation/Withdrawal Criteria

Not applicable to the present database study, which is completely observational and will not affect past, current or future practice/treatment in any way.

# **6.1.** Discontinuation of Study Treatment

Not applicable to the present database study, which is completely observational and will not affect past, current or future practice/treatment in any way.

# **6.2.** Withdrawal from the Study

Not applicable to the present database study.

## 6.3. Lost to Follow Up

Not applicable to the present database study.

# 7. Study Assessments and Procedures

# 7.1. Efficacy Assessments

Not applicable. No efficacy assessments will take place during this retrospective, observational study. The notion of efficacy is nevertheless represented by an expected decrease in the use of asthma rescue medications during the mepolizumab exposure period.

#### 7.2. Adverse Events

This study will be performed exclusively using French national claims database data (SNDS). As a non-interventional study based on secondary use of of medico-administrative data, it meets requirements for a 'European Network of Centers for Pharmacoepidemiology and Pharmacovigilance (EnCEPP) study'. Safety-relevant results will be presented as aggregated data only.

#### 7.3. Treatment of Overdose

Not applicable to the present database study, which is completely observational and will not affect past, current or future practice/treatment in any way.

#### 7.4. Pharmacokinetics

Pharmacokinetic parameters are not evaluated in this study.

## 7.5. Pharmacodynamics

Pharmacodynamic parameters are not evaluated in this study.

### 7.6. Genetics

Genetic evaluations will not be performed in this study.

#### 7.7. Biomarkers

In this non-interventional database study, biomarkers will not be evaluated.

## 7.8. Medical Resource Utilization and Health Economics

No real-time assessments will be made in this retrospective, observational studies. As described in section 4, all data to be analyzed will originate from French national claims databases.

Patients will be identified as beneficiaries within the French National Health Data System [Système National des Données de Santé](SNDS), which covers approximately 66.6 million people, or 99% of the French population (Bezin et al. 2017). The SNDS provides access to pseudonymised health data from 3 databases ('Composantes Du SNDS | SNDS' n.d.; Bezin et al. 2017). (i) The SNIIRAM (Système National d'Information Inter Régimes de l'Assurance Maladie): the main health care claims database. It provides all reimbursed outpatient and inpatient care for the 3 main French claims systems (CNAM, RSI and MSA) and almost all the smaller systems. (ii) The PMSI (Programme de Médicalisation des Systèmes d'Information) (Boudemaghe and Belhadj 2017) contains information on all reimbursed inpatient care for all beneficiaries, and for hospitals and public or private all care facilities. (iii) The BMCD (Base de données sur les causes médicales de décès) from the national death registry (CepiDC, Inserm) provides causes of death.

The vast majority of variables used in this study correspond to health resource usage and associated costs.

#### 8. Statistical Considerations

# **8.1.** Sample Size Determination

This study is primarily descriptive and the identification of beneficiaries receiving mepolizumab in the SNDS will be exhaustive. In this context, traditional sample size calculations are not appropriate/unnecessary.

A first, preliminary analysis of the EGB, a 1/97th random permanent sample of the SNIIRAM French national database (Bezin et al. 2017), currently yields 29 beneficiaries having received mepolizumab during the 11 month period starting in February 2018 and ending in December 2018. We therefore aim to analyze data for approximately  $29 \times 97 = 2813$  beneficiaries receiving mepolizumab with 1 year of follow-up time.

Considering a type I error rate of 5% ( $\alpha$ =0.05), a sample size of 2813 yields *a posteriori* power estimates of 90% or better for cohen's effect sizes superior to 0.063 (Figure 10-1). The latter indicates ample power to detect very small effects (an effect size of 0.2 is considered as "small").

[figure not shown]

Figure 8-1 Effect size versus power for paired t-tests or for paired Wilcoxon tests (non-parametric option) when the type 1 error rate is set at alpha=0.05 and a sample size of 3000 is expected.

NB: This preliminary sample size analysis also served as a testing ground for the primary patient-selection algorithm (based on medication codes UCD 9413850 // code CIP\_C13 3400930038352), which is now finalized.

# 8.2. Populations for Analyses

For purposes of analysis, the following populations are defined:

Population	Description
Evaluable	All lines of data that are included and not excluded will enter the analysis.

# 8.3. Statistical Analyses

### **8.3.1.** General considerations

Children and adult patient data will be analyzed (no age limits will be imposed).

Descriptive statistics for quantitative variables will include sample size and number of missing values, range, median (interquartile range), and mean ± standard deviation. Summary statistics for qualitative variables will include sample size and number of missing values, the frequency and percentage (over non-missing values unless otherwise specified) for each category. All applicable statistical tests will be performed using a bilateral 5% significance level. All confidence intervals (CI) presented will be 95% and two-sided.

The lost to follow-up patients (e.g. exit from one of the insurance schemes available in the SNDS, expatriation with exit from French insurance schemes) will not be included in the study. No replacement of missing values will be performed. For a given patient with a complete follow-up period, all reimbursed healthcare consumptions are reported in the database.

### 8.3.1.1. Mepolizumab exposure

Mepolizumab exposure will be characterized by cumulative numbers of injections and dosage.

Medication persistence is defined as the duration from T0 to the discontinuation of therapy (Cramer et al. 2008)(or the end of follow-up for the present study).

The proportion of days of follow-up covered (PDC) by mepolizumab (or the anologous medication possession ratio for dispensations) will also be calculated as the best available proxy for adherence and an important covariate for analyses or defining subgroups.

If mepolizumab is administered during a hospital stay, the dispensation might not be captured. This possibility will be explored by juxtaposing uncovered (non-PDC) time with hospital stays and investigating two extreme hypotheses: either all such stays contained the missing administration, versus no such stays contained the missing administration. This will provide minimum and maximum possible ranges for mepolizumab exposure.

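### The planned check for uncaptured in-hospital doses covers only time after the recorded T0, so it cannot show whether T0 itself is late; extending it to the index date is a cheap improvement.

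*Protocol*

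**What the plan says.** Under Describing the population (Section 2), the index date "is defined as the day upon which the beneficiary received a first dose of mepolizumab". Appendix 1 agrees: "The time of the first mepolizumab administration". Sections 3.1 and 5.6 also tie T0 to the first injection.

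The data requirements use a different anchor. Section 4 builds the population around the first filled prescription, and the first exclusion criterion in Section 4.2 reads "Health resource use data covering the 12 months preceding the first filled prescription for mepolizumab are not available". Section 1.3 gives the reason: "Mepolizumab exposure is based solely on its delivery".

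Section 8.3.1.1 then acknowledges a gap: "If mepolizumab is administered during a hospital stay, the dispensation might not be captured". Its response is: "This possibility will be explored by juxtaposing uncovered (non-PDC) time with hospital stays and investigating two extreme hypotheses". Under one hypothesis every such stay contained the missing administration; under the other, none did. The stated product is a range for mepolizumab exposure.

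**The concern.** First dose and first captured dispensation are the same day only if the first dose was captured. The protocol says that a dose given during a hospital stay may not be, and nothing in that sentence limits it to later doses. If a patient's first dose was given in hospital and missed, the recorded T0 is a later dispensation. The weeks between the two, and the stay itself, then fall in the year treated as unexposed.

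Every main result is a contrast across T0: total cost (primary endpoint), hospitalisations and days in hospital (secondary), and the cumulative curves of Section 8.3.3, which expect a change of slope at T0. The planned remedy addresses how much drug was received after T0. It does not address whether T0 is in the right place.

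**Working it through.** **Step 1. What the planned check can reach.** Section 8.3.1.1 searches time not covered by mepolizumab. It defines PDC as a proportion of days of follow-up, and follow-up starts at the recorded T0. A dose before the recorded T0 is therefore outside the search under both extreme hypotheses. The output is an exposure range: T0 is not moved, and no cost or hospitalisation comparison is repeated. No other section examines stays shortly before T0.

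**Step 2. Shift per affected patient.** Inputs: a dose every 4 weeks = 28 days (Describing the population); a baseline year of 365 days. With k uncaptured first doses, T0 is about 28k days late, and the share of baseline that is treated time is 28k/365:
- k = 1: 28/365 = 7.7%
- k = 2: 56/365 = 15.3%
- k = 3: 84/365 = 23.0%

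**Step 3. Effect on the count of stays.** By the protocol's own condition, the missed dose was given during a stay. Counted from the true T0, that stay belongs to exposure; counted from the late T0, it belongs to baseline. This is a transfer: baseline gains one stay and exposure loses one, so the after-minus-before difference moves by -2 per affected patient. With affected share s, the cohort mean moves by -2s. The share is not in the protocol, so these values are assumptions:
- s = 5%: -0.10 stays per patient
- s = 10%: -0.20
- s = 20%: -0.40

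This assumes one stay per affected patient, attributed wholly to exposure under the true T0, and ignores the small change at the outer ends of the two years.

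**Step 4. Scale against the study's precision.** Section 8.1 gives N = 29 × 97 = 2813 and power of at least 90% for effect sizes above 0.063. This reproduces:
- Paired t: Φ(0.063 × √2813 - 1.96) = 91.6%.
- Paired Wilcoxon, replacing N by 3N/π: 90.4%.

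The standard error of a paired mean is 1/√2813 = 0.0189 SD of the paired difference. If a share s is shifted by δ SD each, the bias is b = sδ, and the coverage of a nominal 95% interval is 1 - [Φ(b/SE - 1.96) + Φ(-b/SE - 1.96)]:
- s = 5%, δ = 0.2: b = 0.01 SD = 0.53 SE, coverage about 92%.
- s = 10%, δ = 0.5: b = 0.05 SD = 2.65 SE, coverage about 24%.

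Both pairs are assumed. They show that the effect may be negligible or material, and that a large N gives no protection against it.

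**The case against.** The strongest reply is that the gap may be small. The protocol says only that a dispensation might be missed; it does not say that treatment is usually started in hospital. Section 3.2 describes the databases as exhaustive for dispensations. The SNDS description in Section 2 says that inpatient data record a category of costly drugs, and Section 8.1 selects patients on a UCD code as well as a CIP code. All of this stands as a reason to expect partial capture. It does not close the gap: the protocol does not say whether mepolizumab is among the costly drugs, and Section 8.3.1.1 itself leaves the question open.

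A second reply is that the cumulative and 28-day cost-rate curves of Section 8.3.3 could reveal a cluster of stays just before T0. They could, but they neither move T0 nor repeat the comparison.

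A third is that sensitivity analyses are often left to the SAP. Here the protocol already specifies one for this very gap, and the point is that its scope is too narrow.

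Two stronger readings are tempting. A reader might infer that everyone started in hospital has a late T0; only those whose dose was not captured do. A reader might also infer that the error produces an apparent fall in total cost. The documents do not support that: the stay moves into baseline and raises its cost, but treated weeks in baseline may also lower resource use there, so the net direction is not fixed.

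**Conclusion.** The point holds as a cheap improvement to the plan. The two-extremes check bounds exposure after the recorded T0; it does not bound the index date or the before-after results. For affected patients, T0 is about 28 days late per missed dose, 7.7% of the baseline year each, and the stay with the first dose changes sides. For hospital stays the shift favours an apparent fall. For total cost, the primary endpoint, no direction can be claimed. The size across the cohort is unknown because the protocol gives no number of uncaptured in-hospital first doses; the cohort-level figures above are illustrations over assumed shares.

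**What to change.** In Section 8.3.1.1, extend the two-extremes exercise to the index date:

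- Flag patients with any hospital stay in the 35 days (28 plus the 7-day leeway) before the first captured dispensation, and report how many there are.
- Keep the main analysis with T0 at the first captured dispensation.
- As a sensitivity analysis, move T0 to that stay for flagged patients, repeat the primary cost comparison and the hospitalisation comparisons, and show both sets of results side by side. State in advance which date of the stay is used.
- Keep re-dated patients in the cohort even if the moved T0 falls before February 2018.
- Extract a little data before February 2017 so that their baseline year is complete. For a recorded T0 of 1 February 2018, moving back 35 days gives 28 December 2017, so baseline would start on 28 December 2016.

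The cost is one more run of the planned comparisons and a slightly earlier extraction start, which should be settled before the data request. The downside is that some stays will be true exacerbations and will be re-dated wrongly, so the result is a bound and should not replace the main analysis. A patient with several missed doses would be flagged but moved back only as far as a stay within the 35 days.
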